Overall, the PCC group received a median (IQR) of 24.9 (21.8–27.0) IU/kg of PCC [two patients (3.7%; 95% CI 0.4–12.7%) required FP after PCC], and the FP group received a median (IQR) of 12.5 (10.0–15.0) mL/kg of FP [four patients (8.5%; 95% CI 2.4–20.4%) required >2 doses of FP]. Median (IQR) 12-hour chest tube drainage was 310 (250–455) mL and 500 (310–750) mL in the PCC and FP groups, respectively ($P<0.001$). One of the primary measures of haemostatic effects was treatment response, based on receipt of any haemostatic therapies from 60 minutes to 4 and 24 hours after initiation of study treatment. Haemostatic therapy was not required at the 4-hour time point for 43 patients (79.6%) in the PCC group and 32 patients (68.1%) in the FP group ($P=0.25$), nor at the 24-hour time point for 41 patients (75.9%) in the PCC group and 31 patients (66.0%) in the FP group ($P=0.28$). Another primary outcome measure was cumulative and individual allogeneic blood component units administered within 24 hours after the start of surgery. Median (IQR) 24-hour post-bypass cumulative allogeneic transfusions, including red cells, platelets and all (IMP + non-IMP) FP were 5.0 (4.0–9.0) units in the PCC group and 12.0 (7.0–19.0) in the FP group; ratio 0.56, 95% CI 0.43–0.73; $P<0.001$. Excluding IMP FP, the median (IQR) cumulative allogeneic transfusions were 5.0 (4.0–9.0) and 8.0 (4.0–15.0) units, respectively; ratio 0.78, 95% CI 0.58–1.06; $P=0.11$. For red cells alone, the median (IQR) was 1.0 (0.0–2.0) and 2.0 (1.0–3.0) units, respectively; ratio 0.53, 95% CI 0.36–0.78; $P<0.001$. Adverse event profiles were similar.

This pilot study showed that 4-factor PCC may be a suitable substitute for FP for mitigation of bleeding in cardiac surgery and validated the study methodology and dosing that will be used for the proposed trial. It also clearly illustrated that a large, multicentre, confirmatory trial is warranted to determine the relative risk-benefit profiles of these two therapeutics.

Purpose of the Study

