To ensure that the results of the study are clinically relevant and generalisable, the LEX-211 study aims to include a wide spectrum of cardiac surgery patients (including simple or complex procedures and elective or non-elective procedures). In particular, two important, interrelated risk factors for haemorrhage due to coagulation factor deficiency are complex surgery and prolonged CPB duration. Complex surgeries include combined procedures (e.g., CABG + valve or multiple valves) and surgery on the aorta, and these are the procedures that also require prolonged CPB duration. Another equally important risk factor is non-elective surgery, as the risk of haemorrhage is substantially higher in patients who require emergency cardiac surgery. Thus, it is important to include patients undergoing complex or non-elective cardiac surgery in clinical studies on management of haemorrhage during cardiac surgery to ensure that the findings are clinically relevant and generalisable to this important population.

Therefore, the study will include adult patients undergoing any type of cardiac surgery (excluding those undergoing highly specialised procedures where there is wide variability in clinical practice, such as heart transplantation) who require coagulation factor replacement due to haemorrhage in the operating room, post-CPB. Given that patients undergoing isolated CABG are at low risk for haemorrhage, with approximately 2.5–7.5% receiving coagulation factor replacement with FP [77], it is anticipated that the study will primarily include patients who develop haemorrhage after complex surgeries, non-elective surgery or both. Overall, cardiac surgery patients who require coagulation factor replacement due to haemorrhage represent a small proportion of those undergoing cardiac surgery. In the FARES pilot study, patients for whom coagulation factor replacement was ordered during surgery for management of bleeding represented approximately 12% (169 of 1360) of all adults who underwent cardiac surgery at the two study centres in Canada during the study period [58].

Importantly, the study will not involve treating patients prophylactically before surgery as a Cochrane review found no evidence to support the prophylactic administration of FP to patients without coagulopathy undergoing elective cardiac surgery [30].

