3.3.1.5 Recruitment and Informed Consent

This is a pragmatic trial that compares two coagulation factor replacement therapies that are currently routinely used for the study indication in multiple regions globally and in various settings. It is not expected that participating in the trial will pose any risks to patients.

All patients ≥ 18 years old undergoing cardiac surgery with CPB at the study centres will be offered the chance to participate in the study prior to their surgery. Voluntarily given, written, informed consent will be obtained from the patient before the study procedures start. Once consent has been obtained and the patient enrolled into the study, eligibility according to inclusion criteria 1 and 4 (i.e., patients ≥ 18 years old, undergoing any index cardiac surgery employing CPB, who have provided informed consent) and the exclusion criteria will be confirmed. If screening is performed before the day of surgery, exclusion criterion 3 (i.e., severe right heart failure [clinical diagnosis \pm echocardiography]) will be rechecked on the day of surgery².

Only patients who require coagulation factor replacement therapy during surgery will be randomised, receive study drug, and undergo the proceeding visits and assessments. When the first order for PCC or FP is received by the blood bank/pharmacy while the patient is in the operating room, the blood bank/pharmacy technologist will confirm patient eligibility with the clinical team. Following confirmation of eligibility, the technologist will randomise the patient to PCC or FP according to the randomisation and dosing schedule.

²In Canada, informed consent will be obtained after randomisation, in accordance with Article 3.7A of the 2018 Tri-Council Policy Statement on the Ethical Conduct for Research Involving Humans.

Randomisation (1:1) will continue until at least 410 evaluable patients are obtained (205 patients per group).

3.3.1.6 *Blinding*

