9.1 Determination of Sample Size

The analysis of the primary efficacy endpoint will involve comparison of haemostatic treatment response to IMP, defined as 'effective' if no additional haemostatic intervention, such as administration of any systemic haemostatic agents (including platelets, cryoprecipitate, fibrinogen concentrate, activated recombinant factor VII, other coagulation factor products or a second dose of IMP) or any haemostatic interventions (including surgical re-opening for bleeding) is required from 60 minutes to 24 hours after initiation of the first dose of IMP.

Patients categorised as having an 'ineffective' haemostatic treatment response to IMP, due to requiring administration of any haemostatic intervention, including a second dose of IMP, in the time window from 60 minutes to 24 hours after initiation of the first IMP dose, will be considered as treatment failures.

Of the more than 100 patients studied in the FARES pilot study, approximately 75% of patients in the PCC group and 65% in the FP group demonstrated haemostatic treatment response from 60 minutes to 24 hours after initiation of the first IMP dose [58]. Using a more conservative estimate of 70% versus 65%, it is estimated that 410 patients will be required to demonstrate non-inferiority with a one-sided α of 0.025, power of $\geq 90\%$ and non-inferiority margin of 0.10 when using a Farrington-Manning score test.

It is anticipated that up to 20% of randomised patients may not meet administration criteria (based on objective Bleeding Severity Scale and INR) due to cessation of haemorrhage between randomisation and delivery of IMP to the operating room and therefore will not receive the therapy.

An administrative unblinded interim analysis will be carried out after 200 evaluable patients have been randomised and treated and will be used to re-estimate the sample size or stop for futility (non-binding) (**Section 9.4**). Patient recruitment will continue during the conduct of the interim analysis. The sample size in the second stage is limited to 210–800 evaluable patients. Accounting for drop-outs as described above, the total sample size will range between 513–1250 if the study is not stopped for futility at the interim (see table below).

	Stage 1	Stage 2 – Minimum	Stage 2 – Maximum	Total - Maximum
Evaluable patients	200	210	800	1000
Sample size including 20% dropouts	250	263	1000	1250

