9.2 Statistical Analysis

A formal SAP describing all details of the analyses to be performed will be prepared by the study statistician and approved by the Sponsor prior to study initiation.

The non-inferiority of the primary endpoint 'haemostatic response' will be tested between the treatment groups by means of a Farrington-Manning score test with a non-inferiority margin of 0.10 at a one-sided significance level alpha of 2.5%, testing the null hypothesis as follows:

$$H_0: p(PCC) \leq p(FP) - 0.10$$

will be tested against the alternative

$$H_1: p(PCC) > p(FP) - 0.10$$

where $p(PCC)$ and $p(FP)$ denote the haemostatic response proportions in the PCC and FP treatment groups, respectively.

At the end of the trial, the inverse normal test statistic with equal weights given by

$$(\Phi^{-1}(1 - p_1) + \Phi^{-1}(1 - p_2))/\sqrt{2}$$

is calculated, where p_1 and p_2 denote the p-values for testing the non-inferiority null hypothesis for the first and the second stage of the trial, respectively. If the test statistic exceeds the value 1.96, non-inferiority is demonstrated (see [94]).

Only in case that non-inferiority is demonstrated at the second stage of the study, i.e., the null hypothesis is rejected at the one-sided 2.5% level of significance, superiority of PCC with regard to the primary endpoint will be investigated:

$$H_0: p(PCC) \leq p(FP)$$

will be tested against the alternative

$$H_1: p(PCC) > p(FP)$$

The Farrington-Manning score test will be used to calculate a two-sided 95% confidence interval based on the inverse normal test statistic as given above. This confidence interval corresponds with the test decision for showing non-inferiority and/or superiority [95]. This hierarchical test procedure allows to perform the superiority test at the full alpha of 2.5%.

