9.2.2 Efficacy Analysis Plan

Descriptive statistics or frequency tables will be presented for all efficacy data in addition to the inferences performed. Simple tests of comparison will be used to compare endpoints between the two groups. The summary tables and exploratory inferences will be chosen according to the scaling level of the measurements. Frequency tables will be provided for categorical responses and summary statistics for continuous data. The SAP will detail all analyses, including exploratory analyses (e.g., *p*-values and confidence intervals) to be undertaken.

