The analysis of categorical variables (S1, S3, S8, S9, S10, S11, S12) will present relative frequency tables and estimates of the proportions with 95% confidence intervals separately in the treatment groups. The proportions will be compared between the treatment groups in the context of a logistic regression model.

The analysis of continuous variables (S2, S13, S14, S15) will present descriptive statistics of the sampling distribution and the differences between treatment groups. Also, 95% confidence intervals and results of F-test of the treatment group differences will be reported in the context of an ANOVA model.

The analysis of integer count variables (S4, S5, S6, S7) will present descriptive statistics of the sampling distribution and the differences between treatment groups. Treatment group comparisons for variables (S4, S5, S6, S7) will be performed in the context of a counting regression model for the ABCs and their components (SAS PROC GENMOD with Negative-Binomial distribution). Tests and 95% confidence intervals for the treatment group differences will be derived from this statistical model and reported.

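### SAP 10.3 names no covariates for chest-tube drainage (S2) or transfusion counts (S4–S7), so these comparisons give up some precision that the collected risk factors could supply

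*SAP*

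**What the plan says.** SAP 10.3 sorts the secondary endpoints by data type. For the continuous ones, including drainage at 12 and 24 hours (S2): "Also, 95% confidence intervals and results of F-test of the treatment group differences will be reported in the context of an ANOVA model". The component counts S4–S7 are compared with a negative-binomial regression. No covariate, centre term or transformation is named for either, and SAP Appendix 1 contains no derivation for drainage. Protocol 9.2.2 points the same way: "Simple tests of comparison will be used to compare endpoints between the two groups".

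Elsewhere the documents supply the prognostic factors. Protocol 1.1 says that "two important, interrelated risk factors for haemorrhage due to coagulation factor deficiency are complex surgery and prolonged CPB duration", and it gives non-elective surgery equal weight. Protocol 7.2.2.2 collects procedure details and bypass times. Protocol 9.2.1 and SAP 6.6 use urgency, complexity and bypass duration, but only to define subgroups. Randomisation is stratified by centre (Protocol 4.4 and 9.3). Site appears in the SAP's efficacy analyses only as a descriptive summary of the primary endpoint (SAP 10.4).

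**The concern.** When strong predictors of bleeding are known and recorded, leaving them out of a model for bleeding volume or transfused units leaves explainable variation in the error term. Intervals are then wider than the same data allow. Leaving out the stratification factor has the same effect if centres differ in drainage or transfusion practice.

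Reduced drainage is a secondary objective in its own right, and Protocol 3.3.3 lists transfusion amounts among the supportive evidence for haemostatic efficacy. There is also a pre-specification point: if covariates were intended, the SAP does not say which, and that choice should not be made after unblinding.

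**Working it through.** **1. Sample size used below.** The documents give no sample size, standard deviation or power for drainage or counts, so I use the primary endpoint's figure: "Using a more conservative estimate of 70% versus 65%, it is estimated that 410 patients will be required to demonstrate non-inferiority". The closed-form Farrington–Manning calculation (70% v 65%, margin 0.10, one-sided 0.025, 90% power) gives 204.4, so 205 per arm, with power 90.1%. With 20% dropout, 410/0.8 = 512.5, or 513. Both stated figures reproduce.

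**2. Gain from adjustment.** If baseline factors explain a share R² of the outcome variance, the standard error is multiplied by √(1−R²), and the equivalent sample size by 1/(1−R²). R² is not in the documents; 5–20% is an assumption.

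| Assumed R² | SE factor | Fall in SE | Equivalent sample size |
|---|---|---|---|
| 0.05 | 0.975 | 2.5% | ×1.05 |
| 0.10 | 0.949 | 5% | ×1.11 |
| 0.20 | 0.894 | 11% | ×1.25 |

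This formula belongs to the linear model. For the counts, a separate negative-binomial check gave standard errors 3–16% smaller, again under assumed covariate strengths.

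**3. What that means for drainage in mL.** Pilot values (Protocol 1.1): "Median (IQR) 12-hour chest tube drainage was 310 (250–455) mL and 500 (310–750) mL" for PCC and FP. Simulation used log-normal data, a common log SD of 0.56, 205 per arm and two-sided 5%, with R² defined on the log scale. The ratios other than the pilot's are illustrative.

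| True median ratio | Unadjusted power | Adjusted, R² 0.10 | Adjusted, R² 0.20 |
|---|---|---|---|
| 0.62 (pilot) | about 100% | not run | about 100% |
| 0.80 | 97% | 98% | 99% |
| 0.85 | 77–78% | 82% | 84% |
| 0.90 | 41–43% | 46% | 47% |

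Simulated type I error was 4.8% unadjusted and 4.7% adjusted.

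**4. What it means for counts.** Take S5 (non-IMP components). The pilot ratio was 0.78 (95% CI 0.58–1.06).
- SE of the log ratio: ln(1.06/0.58)/3.92 = 0.154.
- Rescaled from 54 and 47 patients to 205 per arm, assuming the same dispersion: 0.154 × √[(2/205)/(1/54 + 1/47)] = 0.154 × 0.495 = 0.076.
- Power at ratio 0.78: Φ(0.248/0.076 − 1.96) ≈ 90%.
- Power at ratio 0.85: Φ(0.163/0.076 − 1.96) ≈ 57%. This rises to 61% or 66% if 10% or 20% of the variance is removed.

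**5. Should drainage move to the log scale?** From the pilot quartiles, log SD = ln(Q3/Q1)/1.349:
- PCC: ln(455/250)/1.349 = 0.44.
- FP: ln(750/310)/1.349 = 0.65.

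If both arms shared one log SD of 0.44, 0.56 or 0.65, the mL analysis would keep 91%, 85% or 80% of the log analysis's efficiency. But the two SDs differ. With 0.44 and 0.65, 205 per arm, FP median 500 mL and median ratio 0.85:
- Log: z = 0.1625/√[(0.444² + 0.655²)/205] = 0.1625/0.0553 = 2.94, power about 84%.
- mL: the log-normal means are 500·exp(0.655²/2) ≈ 620 and 425·exp(0.444²/2) ≈ 469, with SDs of about 453 and 219. So z = 151/√[(453² + 219²)/205] = 151/35.1 ≈ 4.3, power about 99%.
- Equal mean mL in both arms: the log means still differ by (0.655² − 0.444²)/2 = 0.116. So z = 0.116/0.0553 = 2.10, and the log test rejects about 55% of the time.

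The ranking reverses, because the two scales test different quantities.

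**The case against.** The strongest reply is that nothing is broken. SAP 10.3 introduces these endpoints as ones to be explored, an unadjusted comparison of randomised groups is valid, and the primary test is untouched. The pilot drainage effect would be detected under any model. The size of the gain rests on an R² that the documents do not supply. All of this stands, and it keeps the point small. It does not remove it, because the change needs no new patients and the factors are the ones the protocol itself calls important.

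It can also be said that an ANOVA or a regression model does not exclude further terms. That is fair: what the text establishes is that the terms are unspecified. The wording "Simple tests of comparison will be used to compare endpoints between the two groups" favours a treatment-only reading, and the remedy is the same either way.

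A third objection concerns bypass duration. Protocol 6.1.3 records bypass start and end times at Visit 2, after randomisation, and no section says that the recorded duration stops at randomisation. A patient who returns to bypass would have a duration partly determined after assignment. This stands and is met by restricting the covariate.

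A reader might also infer that drainage is so skewed that the mL analysis is inefficient and should be replaced by a log analysis. The documents do not support that. The pilot quartile skewness is clear in the PCC arm (0.41) but mild in the FP arm (0.14), and the PCC arm stays skewed after taking logs (0.28). The efficiency argument needs a common log SD, which the pilot quartiles do not show. With 54 and 47 patients those quartiles are noisy, so they do not prove mL better either. For the counts, the negative-binomial model already allows for skew.

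**Conclusion.** The point holds as a modest loss of precision and a gap in specification. SAP 10.3 names no covariate for S2 or S4–S7, although the main bleeding risk factors are identified, planned as subgroup factors, and accompanied by a stratification factor that the models also omit. For drainage, the gain is a fall in standard error of about 2.5–11% if those factors explain 5–20% of the variance. That range is assumed, and it does not count any contribution from centre. The practical benefit is confined to effects smaller than the pilot's: for drainage at a ratio of 0.85, power would rise from about 77% to 82–84% for R² of 0.10–0.20, under the log-normal assumption. Neither bias nor inflated type I error follows from the present plan, and the case for changing the main scale of S2 is not made. The amendment is worth making because it is cheap.

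**What to change.** In SAP 10.3, add these terms to the S2 ANOVA and the S4–S7 negative-binomial models:
- complexity (simple/complex) and urgency (elective/non-elective), as defined for the subgroups in SAP 6.6;
- bypass duration accrued before the first coagulation-factor order, as a continuous covariate;
- centre, with a stated rule for pooling small centres.

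Keep the unadjusted comparison as a sensitivity analysis. Keep mL as the main scale for S2. A log-scale ratio of geometric means may be added as a sensitivity analysis only, with a rule for zero values and a note that it estimates a different quantity from the difference in mean mL.

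The cost is a paragraph of SAP text, a few model terms and one derivation for pre-order bypass time. Rarely used individual components in S7 may not support all terms, so the SAP should also state the order in which terms are dropped if a model fails to converge. The sample size, the data collected and the primary analysis do not change.

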6 STUDY CONDUCT

All patients ≥ 18 years old undergoing cardiac surgery with CPB at the study centres will be the potential patients in the study. Voluntarily given, written, informed consent will be obtained from the patient. Once consent has been obtained and the patients enrolled into the study, eligibility according to inclusion criteria 1 and 4 (i.e., patients ≥ 18 years old, undergoing any index cardiac surgery employing CPB, who have provided informed consent) and the exclusion criteria will be determined. If screening is performed before the day of surgery, exclusion criterion 3 (i.e., severe right heart failure [clinical diagnosis \pm echocardiography]) will be rechecked on the day of surgery.

Only patients who require coagulation factor replacement therapy during surgery will be randomised, receive study drug, and undergo the proceeding visits and assessments.

When the first order for PCC or FP is received by the blood bank/pharmacy while the patient is in the operating room, the blood bank/pharmacy technologist will confirm patient eligibility with the clinical team. Following confirmation of eligibility, the technologist will randomise the patient to PCC or FP according to the randomisation and dosing schedule and prepare and release the IMP in a tamper sealed container (with weight device in PCC containing boxes to ensure adequate concealment). Operating room personnel will remain blinded until the decision to administer the IMP is made.

IMP can be administered if bleeding is severe enough to necessitate IMP (meaning at least a grade 2 level [moderate] bleeding according to the validated Bleeding Severity Scale [78] – see Appendix 1), heparin is adequately reversed (confirmed by the return of post-protamine ACT to within 10% of pre-pump ACT) and INR is ≥ 1.5 (using the Hemochron Signature Elite; Instrumentation Laboratory). IMP can also be administered if bleeding is severe enough to require urgent therapy, in which case treatment can be initiated irrespective of the INR value. Once the decision is made to administer the IMP, the administering clinician will break the seal on the container, carry out routine safety checks, and initiate IMP administration according to the weight-based dosing recommendations: For *Octaplex*: 1500 IU if ≤ 60 kg; 2000 IU if >60 kg. For FP: 3 U if ≤ 60 kg; 4 U if >60 kg.

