6.1.2 Visit 1 (POD 0 pre-randomization): Pre-randomisation visit (blood bank/pharmacy)

First coagulation factor replacement order from the surgical team received at the blood bank/pharmacy

Surgical staff will confirm protocol criteria before the blood bank/pharmacy order is made.

Surgical staff will record the patient's body weight.

The blood bank/pharmacy technologist will confirm and document the following:

- All eligibility criteria are met

The blood bank/pharmacy technologist will then randomise patients to Octaplex or FP according to the randomisation schedule and prepare and release the product.

Note; if subsequent coagulation factor replacement orders are made within 24 hours from IMP initiation, the blood bank/pharmacy technologist will confirm and document that all contents of the order have been administered.

6.1.3 Visit 2 (POD 0 post-randomization and POD 1): First visit after IMP initiation (0 to 24 hours after IMP initiation)

For any specified activity that cannot be completed during the first visit after IMP initiation, additional visits will be made on postoperative day 1 until all study data are obtained.

- Collect baseline data
 - Demographics (sex, age, height and Body Mass Index [BMI])
 - Medical history
 - Preoperative concomitant medications
 - Laboratory assessments where available as part of routine care
 - Clinical chemistry (sodium, potassium, chloride, bicarbonate, pH)
 - Haematology (complete blood count)

- Safety laboratory analyses if available (creatinine, liver function tests [ALT, ALP], bilirubin, troponin)
- Administer first dose of IMP
- Collect surgical data
 - Intraoperative concomitant medications
 - CPB start and end times
 - Cross-clamp time
 - Circulatory arrest start and end times
 - Fluid intake and output monitoring
 - Inotropes and vasopressors
 - Start and end time of IMP administration
 - Length of stay in the OR
- Collect laboratory assessments where available as part of routine care
 - Clinical chemistry (sodium, potassium, chloride, bicarbonate, pH)
 - Haematology (complete blood count)
 - Any coagulation measures (e.g. PT, aPTT, INR, plasma fibrinogen level, ROTEM EXTEM CT and MCF, ROTEM FIBTEM MCF, platelet count, platelet function) measured from within 75 minutes before to within 75 minutes after IMP initiation.
 - Safety laboratory analyses if available (creatinine, liver function tests [ALT, ALP], bilirubin, troponin)

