- Measure haemoglobin within 30 ± 15 minutes before and at 60 ± 15 minutes after IMP initiation
- Measure INR within 30 ± 15 minutes before and at 60 ± 15 minutes after IMP initiation and document results
- Administer second dose of IMP, if needed
- Collect all transfusions and haemostatic therapies
- Collect chest tube drainage at 1, 6, 12 and 24 hours after chest closure
- Measure haemoglobin at 24 hours ± 1 hour after IMP initiation and document results
- Collect extubation time
- Collect concomitant medications
- Collect AEs and SAEs

6.1.4 Visit 3 (POD 2-7): Days 2-7 after IMP initiation (or at discharge, if earlier)

- Collect daily laboratory assessments where available as part of routine care
 - Chemistry (sodium, potassium, chloride, bicarbonate, pH)

- Haematology (complete blood count)
- Coagulation profile (e.g. PT, aPTT, INR, plasma fibrinogen level, ROTEM EXTEM CT and MCF, ROTEM FIBTEM MCF platelet count, platelet function)
- Safety labs (creatinine, liver function tests [ALT, ALP], bilirubin, troponin)
- Collect all transfusions and haemostatic therapies
- Record incidence of intracerebral haemorrhage, gastrointestinal haemorrhage and surgical re-exploration.
- Collect extubation time (if applicable)
- Collect length of stay in the ICU and hospital (if applicable)
- Collect concomitant medications
- Collect AEs and SAEs

6.1.5 Visit 4 (POD 30): Day 30 after IMP initiation (in person if in hospital, or by phone)

- Collect concomitant medications
- Collect AEs and SAEs
- Collect extubation time (if applicable)
- Collect length of stay in the ICU (if applicable)
- Collect length of stay in the hospital (if hospital stay is extended) and hospital readmissions
- Document patient outcome and survival at 30 days (still in hospital; dead or alive)

After Visit 4 or on POD-30, the clinical study is considered completed for the patient. No further study-related assessments will be performed, unless safety concerns (e.g., ongoing AEs) require follow-up.

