- S9. Comparison of the incidence of administration of non-IMP coagulation factor products – including fibrinogen concentrate and activated recombinant factor VII – during the first 24 hours and 7 days after the start of surgery, after the end of CPB and after IMP initiation, between the *Octaplex* and FP groups.
- S10. Comparison of the incidence of intracerebral haemorrhage during the first 24 hours after start of surgery, after the end of CPB and after IMP initiation between the *Octaplex* and FP groups.
- S11. Comparison of the incidence of gastrointestinal haemorrhage during the first 24 hours after start of surgery, after the end of CPB and after IMP initiation between the *Octaplex* and FP groups.
- S12. Comparison of the incidence of surgical re-exploration for bleeding during the first 24 hours after start of surgery, after the end of CPB and after IMP initiation between the *Octaplex* and FP groups.
- S13. Comparison of the change in INR, from within 30 minutes before to within 60 minutes after the initiation of IMP administration, between the *Octaplex* and FP groups; INR reduction will be considered successful if the magnitude of the reduction is >1.0 or the post-treatment level drops below 1.5.
- S14. Comparison of the changes in other coagulation parameters, including PT, aPTT, fibrinogen activity, ROTEM EXTEM CT and MCF and platelets, from within 75 minutes before to within 75 minutes after the initiation of IMP administration, between the *Octaplex* and FP groups. For a given parameter, if there are multiple results in the window within 75 minutes before to initiation of IMP administration, the most recent result before IMP initiation will be used. If there are multiple results in the window within 75 minutes after the initiation of IMP administration, the earliest result after IMP administration will be used.
- S15. Comparison of time elapsed from initiation of the first dose of IMP to arrival at the ICU room between the *Octaplex* and FP groups. Patients in the ICU at the time of first dose of IMP will be excluded from this analysis.

The following analysis methods will be applied to the different endpoints, according to their data type:

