## 14. Changes from Analyses Specified in the Protocol

The described statistical analyses match those pre-specified in the study protocol.

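### Changes in INR (S13) and coagulation tests (S14) are compared by ANOVA with no pre-IMP covariate: valid, but precision is given up on data already collected

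*SAP*

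**What the plan says.** SAP 10.3 defines S13 as the change in INR and S14 as the changes in PT, aPTT, fibrinogen activity, ROTEM EXTEM CT and MCF, and platelets, each from a pre-IMP to a post-IMP value. For S14 it also settles which earlier result counts when there are several: "the most recent result before IMP initiation will be used". SAP 7.1.1 gives a general baseline definition on the same lines.

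For the continuous endpoints (S2, S13, S14, S15), SAP 10.3 plans descriptive statistics, 95% confidence intervals, and that "results of F-test of the treatment group differences will be reported in the context of an ANOVA model". No model terms are listed.

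No covariate is supplied elsewhere:

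- Protocol 9.2.2: "Simple tests of comparison will be used to compare endpoints between the two groups". It adds: "The SAP will detail all analyses, including exploratory analyses".
- SAP 14: "The described statistical analyses match those pre-specified in the study protocol".
- SAP 10.4 (sensitivity analyses) covers the primary endpoint only.
- The SAP abbreviation list has ANOVA but not ANCOVA.

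On data collection, Protocol 6.1.3 (Visit 2) makes INR mandatory: "Measure INR within 30 ± 15 minutes before and at 60 ± 15 minutes after IMP initiation and document results". The other coagulation tests come under a softer instruction: "Collect laboratory assessments where available as part of routine care". Protocol 6 sets an INR of at least 1.5 among the conditions for giving IMP, but allows an exception for urgent bleeding, "in which case treatment can be initiated irrespective of the INR value". Randomisation is stratified by site (SAP 4.3).

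**The concern.** Subtracting the pre-IMP value is the same as putting it in the model with its slope forced to 1. If the true slope of the post-IMP on the pre-IMP value differs from 1, part of the variation between patients that the pre-IMP value could explain stays in the error term, and the interval for the treatment difference is wider than it need be.

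For INR, a slope below 1 is likely. Patients may start anywhere from near normal to high, and a near-normal INR has little room to fall. This is an inference from the administration rule, not a figure in the documents.

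Only precision is at stake. S13 and S14 are exploratory, but they are the direct laboratory comparison of the two products, and Protocol 3.3.3 counts INR reduction among the supportive evidence of efficacy. S14 is where precision may be shortest, because both values may exist for only some patients.

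**Working it through.** **The plan's own figure.** The documents give no SD, correlation, power or sample size for S13 or S14. The only related figure is the 410 evaluable patients for the primary endpoint (Protocol 9.1). It reproduces. With 70% v 65%, margin 0.10 and one-sided alpha 0.025, the Farrington-Manning restricted proportions are 0.619 and 0.719, so

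n per arm = (1.960·√0.4377 + 1.282·√0.4375)² / 0.15² = 204.4, i.e. 205 per arm, 410 in total, power 0.901.

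This number does not depend on the present point. It serves below only as the largest of three reference sizes.

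**Variance comparison.** Let r be the pre/post correlation within groups and k = SD(post)/SD(pre), both taken as equal in the two arms. In units of the pre-IMP variance:

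- change-score ANOVA: error variance = 1 + k² − 2rk
- ANCOVA: error variance = k²(1 − r²)
- difference between the two = (1 − rk)²

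The ratio is therefore k²(1 − r²)/(1 + k² − 2rk). It cannot exceed 1, and it equals 1 only when the slope rk is 1. At k = 1 it reduces to (1 + r)/2. The CI reduction is 1 − √ratio. The extra patients that ANOVA would need for the same precision are 1/ratio − 1.

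| r (k = 1) | Ratio | CI narrower by | Extra patients needed |
|---|---|---|---|
| 0.3 | 0.65 | 19.4% | 54% |
| 0.5 | 0.75 | 13.4% | 33% |
| 0.7 | 0.85 | 7.8% | 18% |
| 0.9 | 0.95 | 2.5% | 5% |

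For r from 0.3 to 0.9, the CI is 25–32% narrower at k = 0.75 and 0–11% narrower at k = 1.25. The zero falls at r = 0.8, where the slope is 0.8 × 1.25 = 1.

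**Check by simulation (3,000 trials of 410 patients, k = 1).** The ANCOVA/ANOVA variance ratios were 0.656, 0.738 and 0.863 at r = 0.3, 0.5 and 0.7, against 0.65, 0.75 and 0.85 from the formula. The planned ANOVA was unbiased, with type I error 0.045–0.046 at a nominal 0.05.

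**Adding site, and fewer complete pairs.** Assumptions: 12 sites holding 2–20% of patients each, 1:1 allocation within site, no differences between sites, and sites with fewer than 10 complete pairs pooled. Both values are present for all patients, a random half or a random quarter (3,000 trials per setting). CI reduction at k = 1, without / with the site term:

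| Patients with both values | r = 0.3 | r = 0.5 | r = 0.7 | r = 0.9 |
|---|---|---|---|---|
| 410 | 19.3 / 19.2% | 13.3 / 13.3% | 7.7 / 7.6% | 2.4 / 2.4% |
| 205 | 19.2 / 18.3% | 13.2 / 12.2% | 7.6 / 6.6% | 2.3 / 1.2% |
| 102 | 18.9 / 17.6% | 12.9 / 11.3% | 7.4 / 5.8% | 2.0 / 0.4% |

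Nearly all the gain comes from the pre-IMP value. When sites do not differ, the site term costs at most 0.1 points at 410 patients, about 1 at 205 and 1.3–1.7 at 102. In the no-gain case (r = 0.8, k = 1.25), the CI with the pre-IMP value and site is wider by 0.2%, 1.4% and 2.2% at the three sizes.

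**Coverage of the 95% CI.** Change score 0.946–0.957; ANCOVA 0.946–0.959, with or without site. With skewed values (shifted log-normal, 410 patients, 5,000 trials): change score 0.950–0.954, ANCOVA 0.948–0.955.

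**The case against.** The strongest reply is that nothing here is an error. Change-score ANOVA is a recognised and unbiased analysis under randomisation, and the endpoints are exploratory. That is correct, and it keeps this a point to consider rather than a defect.

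Second, the missing covariate is read from silence: SAP 10.3 lists no terms for any of its models. This also stands as a limit. The unadjusted reading is the natural one given Protocol 9.2.2 and SAP 14, but if an adjusted model was intended, the same sentence is still needed to say so.

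Third, the size of the gain cannot be fixed from the documents, the slope argument is made for INR only, and no simulation built in a floor on the INR response. All true. The closed form uses only r and k, so a floor would act through those two quantities, but their values remain unknown. Hence the ranges, including the case of no gain.

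Fourth, the site term brings no gain in these calculations. That is so when sites do not differ, which is what was assumed. Site is proposed because it is the randomisation stratum. The main recommendation, the pre-IMP value, does not depend on it.

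Fifth, the SAP is already at version 5.0 (28-Oct-2024), and SAP 7.5 says it is finalised before any unblinded analysis, while the plan includes an unblinded interim. The timing is late. But SAP 7.4 has the interim done by an independent statistician, with unblinded information going only to the IDSMC, so a change made before the unblinded final analysis can still count as pre-specified.

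**Conclusion.** The point holds as a low-weight improvement. The planned comparison of S13 and S14 is valid, but it is less precise than the same patients allow unless the post-on-pre slope is 1. With equal pre- and post-IMP SDs, the interval would be 2.5–19.4% narrower for correlations from 0.9 down to 0.3. Across SD ratios of 0.75 to 1.25 the range is 0–32%. The largest loss found, with site in the model, about 102 pairs and a true slope of 1, is a CI 2.2% wider.

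These sizes rest on assumed values of r and k, taken as equal in the two arms, and on assumed site sizes with no site effects. The point does not extend to S2 and S15, which have no pre-IMP value of the same measure.

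**What to change.** Before the unblinded final analysis, state in SAP 10.3 that S13 and S14 are analysed by ANCOVA with treatment, the pre-IMP value and site. Pool small sites by a pre-stated rule, for example those with fewer than 10 patients having both values for that parameter. Keep the F-test and the 95% CI for the treatment difference. The endpoints stay as defined: with the pre-IMP value in the model, analysing the change or the post-IMP value gives the same treatment difference, since only the covariate's slope shifts by 1. The unadjusted ANOVA can remain as a supportive analysis.

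Leave the primary Farrington-Manning and inverse normal test unchanged. A site-stratified Mantel-Haenszel risk difference within each stage could be added to SAP 10.4 as a sensitivity analysis of the primary endpoint. That is optional and separate from this point.

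The cost is one sentence in SAP 10.3, one line in SAP 14 recording the departure from simple tests, the programming, and a new SAP version agreed with the sponsor. Protocol 9.2.2 leaves the detail of exploratory analyses to the SAP. No new data are needed, and no patient with a change score drops out. After the unblinded final analysis, an adjusted result could only be reported as post hoc.
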